**Randomization to Stage 2 Treatments for LDX and CBT+LDX (Stage 1) “Responders”.**

“Responders” to Stage 1 LDX (i.e., LDX and CBT+LDX) treatments will be defined as 65% or greater reduction in binge-eating. This cut-point is based on reliable findings regarding prognostic significance of such reductions ([name] et al., 2006; 2012) and supported by recent report on “time course of the effects of LDX” (McElroy et al., 2017). “Responders” will be randomized in equal proportions (using stratified blocked randomization with Stage 1 treatment as a stratifying variable) to LDX or placebo (double-blind) for 12 weeks.

**CBT Treatment Protocol.** CBT will be delivered by trained and monitored research clinicians following manualized protocols we have used successfully in previous RCTs (e.g., [name] et al., 2005, [name] et al., 2011). CBT will be delivered in individual sessions weekly for 12 weeks following CBT manuals based on Fairburn et al (1993) used in our RCTs ([name] et al., 2005, 2011) which are similar to those used in major RCTs testing CBT delivered via 12-24 weeks (Wilfley et al., 2002; Wilson et al., 2010). The CBT manuals provide detailing session-by-session procedures for clinicians and parallel guides are provided to the patients to facilitate homework and mastery of the material. CBT, a specialist focal treatment, consists of

three overlapping phases. Phase one involves establishing a collaborative therapeutic relationship while focusing on educating the patient about the nature of binge-eating and factors thought to maintain the problem. Specific behavioral strategies (e.g., self-monitoring) are used to help patients identify problematic eating patterns while establishing a normal structured eating pattern. Phase two integrates cognitive restructuring procedures, where patients learn to identify and challenge maladaptive cognitions regarding eating and weight/shape and thoughts that trigger binge-eating. Phase three focuses on maintenance of change and relapse prevention.

**LDX Pharmacotherapy Treatment Protocol.** Medication will be double-blind; patients and study staff, physicians and investigators will be blind to medication assignment. **LDX, FDA-approved for BED**, will be prescribed per procedures found to be superior to placebo in two large-scale phase 3 RCTs (McElroy et al., 2015). The LDX (dose-optimization at 50-70mg per day) protocol followed the McElroy et al (2015) RCT findings that 50-70mg/day dosing was significantly superior to 30mg/dosing and to placebo.

During week 1, LDX will be 30 mg/day for initial titration. During week 2, LDX will be titrated to 50mg/day. During weeks 3-4, LDX increases to 70mg will be made based on acceptable tolerability and clinical need. If 70mg is not tolerated, downward titration to 50mg/day can occur. For the remaining treatment (weeks 4-12), the optimized LDX dose (50 or 70 mg/day) will be maintained.

For the Stage 2 randomized maintenance (double-blind) treatment, a similar approach to dose-optimization will be followed for responders. "Responders" re-randomized to LDX will continue taking LDX at the same dose as Stage 1. "Responders" randomized to placebo will be switched from LDX to placebo. Participants will be instructed to take the medication (active or placebo) once daily in the morning.

Safety and tolerability will be assessed during study clinic visits as will clinical compliance with the study medication. During the dose-optimization period, if the patient develops tolerability concerns, dosing can be reduced once to achieve tolerability. If the patient cannot tolerate the medication, has adverse effects, or is non-compliant with medication for > 7 consecutive days, s/he will be discontinued from the medication arm. Physician visits will be brief (10-15 minutes) and focus on compliance with dosing and evaluating side effects without integrating dietary, behavioral, or CBT techniques.

In Stage 1 or Stage 2, participants taking medication for greater than 4 weeks, a taper will be provided (Refer to Minimizing Risk section on page 20 for details).

**Naltrexone/Bupropion (NB) Pharmacotherapy Treatment Protocol.** During Stage 2, "non-responders" will be randomized to NB or placebo. Medication will be double-blind; patients and study staff, physicians and investigators will be blind to medication assignment. NB will be prescribed per FDA-approval for obesity and previous RCTs demonstrating effectiveness for weight loss in obese patients (Greenway et al., 2009, 2010, 2013; Smith et al., 2013; Wadden et al., 2011). "Non-responders" will start taking NB or placebo one week following discontinuation of LDX. NB medication will comprise naltrexone (50 mg/day) combined with bupropion (300 mg/day) taken daily ( matching frequency for placebo). Per previous RCTs, a dosing escalation approach will be used(Greenway et al., 2010; Wadden et al., 2011). See below.

Study Day	Active Group		Placebo Group	
	Naltrexone Capsule	Bupropion XL Capsule	Naltrexone Capsule	Bupropion XL Capsule
1-2	Placebo	150mg	Placebo	Placebo
3-4	Placebo	300mg	Placebo	Placebo
5-study end	50mg	300mg	Placebo	Placebo

This dosing will continue for the remainder of RCT unless a patient develops intolerable side effects. If such occur, the physician may reduce the dosing to achieve tolerability. If the patient cannot tolerate the medication, has adverse effects, or is non-compliant with medication for >7 consecutive days, they will be discontinued from medication arm. Physician visits will be brief (10 -15 minutes), focus on compliance with dosing and evaluating side effects, without using CBT or dietary/behavioral methods. Participants taking medication for greater than 4 weeks, a 7-day taper will be provided (Refer to Minimizing Risk section on page 20 for details).

**Withdrawal From Treatment and Other Treatments.** *Withdrawal/attrition from treatments will be examined.* Use of other treatments during the study will be assessed and considered in analyses. Patients will be asked about all forms of treatments during major assessments. Criteria for removal of patients from the study may include worsening depression, suicidal ideation, intensification of binge eating, or failure to comply with medication. Previous experience suggests that worsening clinical status is rare; in such cases, [name] and study physician would determine whether to remove the person from the study and provide referrals.

**Maintenance of Cohort.** Research staff will form on-going relationships and maintain contact with subjects. Our experience indicates this improves likelihood of participants' willingness to perform follow-up assessments. In addition: (1) At baseline, participants will be interviewed to determine whether they will be available for the entire study duration; (2) Participants will be excluded if unable to comply with birth control methods; (3) Participants will provide names and contact information of at least two relatives or friends and permission to contact them if they move without notifying investigators; (4) At each assessment, participants will be asked if they have plans to move; and (5) We requested funds in the budget to reimburse participants for completion of the assessments.

**Assessment Procedures.** Figure 2 below shows assessment schedule and measures. Major assessment at: baseline, during Stage 1 treatment (month 1, 2), post-Stage 1 treatment (month 3), during Stage 2 treatment (month 4, 5), post-Stage 2 treatment (month 6), and follow-ups at 6- and 12-months after completing Stage 2 treatment (i.e., 18 months after starting treatment). Outcomes assessments will be done by independent evaluators not involved in the treatment delivery and blind to treatment assignments.

**Assessment Training.** Independent assessors will receive training in diagnostic interviews from investigators following established protocols. Interviewers, once certified, will receive ongoing supervision to ensure consistent use and prevent drift. [name] will do inter-rater reliability studies, which he has published for BED ([name] et al., 2004) and psychiatry (Zanarini et al., 2000).

**Eligibility and Baseline Assessment.** Potential subjects will be assessed by clinicians who describe the treatment study and procedures, and obtain informed consent. Baseline assessment (two meetings) will include two interviews, the MINI (Sheehan et al., 2014) and EDE (Fairburn et al., 1993), to generate lifetime and current psychiatric diagnoses and detailed current eating disorder features and (BED) diagnoses.

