Pharmacotherapy with Naltrexone/Bupropion (FDA-Approved for Obesity). In 2014, the FDA approved combination of naltrexone and bupropion for obesity following empirical support from several RCTs performed with obesity (non-BED) (Greenway et al., 2009; Greenway et al., 2010; Smith et al., 2013; Wadden et al., 2011). These RCTs reported significant clinically-meaningful weight losses with sustained-release naltrexone (32 mg/day) plus sustained-release bupropion (360 mg/day) combined in fixed-dose pills ("NB32", which we will refer to as NB medication). For example, Apovian et al (2013), in a study of 1496 obese patients reported significantly greater weight losses relative to placebo (-6.5% vs -1.9% at week 28 and -6.4% vs -1.2% at week 56) and significantly greater likelihood of achieving 5% weight loss (56% vs 18% at 28 weeks). These findings supporting NB medication are quite consistent with earlier large RCTs which reported greater weight loss with NB than placebo (-6.5 vs -1.2% (Greenway et al. 2013); -8.2% vs -2.1% (Smith et al., 2013)). Overall, NB has been well tolerated with the most common adverse event being nausea.

Putative mechanisms of action for Naltrexone and Bupropion seem relevant for binge eating in addition to weight loss. Naltrexone, an opioid receptor antagonist, is approved for treatment of alcohol and opioid dependence (O'Malley, Sinha, [name], et al., 2007). Naltrexone produces weight loss in lab animals but only minimal weight losses in humans (Malcolm et al. 1985; Billes & Greenway, 2013). Bupropion is thought to operate through dopaminergic, noradrenergic, and nicotinic acetyl-cholinergic mechanisms (Slemmer, Martin et al. 2000; Stahl, Pradko et al. 2004; Han, Hwang et al. 2010), may target reward processes that drive eating behaviors, consistent with its FDA indication for treating nicotine dependence and reduced weight gain during smoking cessation (Hurt et al., 1997; Farley et al., 2012). Bupropion has been found to promote weight loss in obesity (Li et al., 2005). White & [name] (2013) first reported preliminary support for a possible (albeit modest) weight loss benefit specifically in obese BED patients.

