LDX is associated with increased risk of serotonin syndrome when co-administered with serotonergic agents, but also during overdosage situations. The potential for a pharmacokinetic interaction exists with co-administration of CYP2D6 inhibitors which may increase the risk with increased exposure to the active metabolite dextroamphetamine.

This study will provide LDX following the same dosing and procedures and time frame (12-weeks) as the large phase 2 study demonstrating safety and optimal dosing and two large phase 3 trials reporting safety and efficacy for BED over 12-week treatments. The same optimal dosing strategy will be used in the Stage 2 maintenance RCT; this delivery safety is further supported by the Hudson et al (2017) report of LDX vs placebo maintenance. LDX is also classified as a DEA-controlled substance and product labeling includes a "Warning" that CNS stimulants have high potential for abuse/dependence.

Bruxism is also a potential rare side effect. History of bruxism in response to a medication will be exclusionary.

**NB:** Naltrexone/Bupropion combination (NB) is FDA approved for the treatment of obesity. NB has demonstrated safety, tolerability, and efficacy for patients with obesity treated over much longer periods of time (>12 months) than in the present study (Greenway et al., 2010). NB was associated with the following side effects in 10% or more of the time and significantly greater than rate in placebo: nausea, headache, constipation, and vomiting. NB was associated with the following side effects less than 10% of cases but significantly more than placebo: dizziness, insomnia, dry mouth, and diarrhea. Less common side effects include risk of seizure, increase in blood pressure and heart rate, hepatotoxicity, and angle-closure glaucoma. Large studies (e.g., Greenway et al., 2010 with N=1742) reported that the proportion of participants reporting a serious adverse event did not differ between Naltrexone/Bupropion and placebo (1.6% versus 1.4%) and none of the observed events were judged to be related to the study. Since one of the study's (Stage 2) medication may be a combination Naltrexone/Bupropion, in keeping with the FDA advisory pertaining to antidepressants, including bupropion, the following information will be included in the study consent forms:

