participants aged 30 years or less (given previous LDX trial report that 0.1% of those patients might have developed such symptoms). Any older patients assessed who are suspected of having such symptoms would also be assessed carefully. We note that subjects with history of psychotic or bipolar illness are excluded from participating and this should minimize such risks. Study clinicians are supervised by licensed psychologists trained and experienced in psychiatric assessment. If participants endorse manic or psychotic symptoms (or any of the other potential symptoms of concern), clinicians will consult with the study investigators for safety management and treatment planning. **Monitoring of depressive symptoms is described below.**

**NB:** The NB pharmacologic treatment protocol (Stage 2 for non-responders to Stage 1) follows the evidence-based dosing that has demonstrated safety, tolerability, and efficacy for obesity treated over much longer periods of time (>12 months) than the present study. Large studies (e.g., Greenway et al., 2010 with N=1742) reported that the proportion of participants reporting a serious adverse event did not differ between Naltrexone/Bupropion and placebo (1.6% versus 1.4%) and none of the observed events were judged to be related to the study. Warning about Opioid Withdrawal: We will include this advisory pertaining to opioid use and examples of opioid-based medications and drugs in the written consent form as well as the verbal consent process: *Naltrexone can cause withdrawal symptoms in individuals who are taking opioid pain medications or drugs. You should not participate and we will not include you in the study if we know or suspect you are using opiate-containing drugs.* In addition to structured MINI and clinical diagnostic interviewing and medical record reviews, we will perform lab test with potential subjects suspected of opiate usage.

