c. Include an appropriate Data and Safety Monitoring Plan. Examples of DSMPs are available here <http://your.yale.edu/policies-procedures/forms/420-fr-01-data-and-safety-monitoring-plans-templates> for

- i. Minimal risk
- ii. Greater than minimal

The principal investigator will be responsible for monitoring the data, assuring protocol compliance, and conducting the safety reviews semi-annually. Although this study qualifies as clinical trial research, it does not meet NIH criteria for Phase III clinical trial research. Nonetheless, this study will be monitored semi-annually by a Data Safety Monitoring Board (DSMB) as the study involves a double-blind placebo

controlled evaluation of medication effects that may involve greater than minimal risk. Adequate surveillance and protections will be put in place to discover adverse events promptly and keep their effects to a minimum. During the review process, the principal investigator and DSMB will evaluate whether the study should continue unchanged, require modification/amendment, or close to enrollment. Either the principal investigator, the IRB or the DSMB have the authority to stop or suspend the study or require modifications.

The risks associated with the current study are deemed greater than minimal. Although we do not view the risks associated with the study medication as minimal risk, the established safety and validity of the LDX (FDA-approval of Vyvanse for BED) and Naltrexone/Bupropion (FDA-approval of Contrave for obesity) medications in RCTs suggest that the study procedures and medications are not high risk.

Although we have assessed the proposed study as one of greater than minimal risk, the potential exists for anticipated and/or unanticipated adverse events, serious or otherwise, to occur since it is not possible to predict with certainty the absolute risk in any given individual. Therefore, we provide a plan for monitoring the data and safety of the proposed study as follows:

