#### **NALTREXONE/BUPROPION (Stage II Medication for Non-Responders)**

In September 2014, the FDA approved (“Contrave”) the combination of naltrexone and bupropion to treat obesity consisting of the following empirical support from several RCTs performed with obesity (but not BED). NB medication will combine the generics naltrexone (50 mg/day) combined with bupropion (300 mg/day) taken daily; matching frequency for placebo).

**Mechanisms of Action.** The putative mechanisms of action for NB seem relevant for binge eating in addition to weight loss. Naltrexone, an opioid receptor antagonist, is approved to treat alcohol and opioid dependence [92]. Naltrexone produces weight loss in lab animals but only minimal weight losses in people [93, 94]. Bupropion operates through dopaminergic, noradrenergic, and nicotinic acetyl-cholinergic mechanisms [51-53]. Bupropion may target reward processes that drive eating behaviors, consistent with its FDA indication for treating nicotine dependence and reduced weight gain during smoking cessation [54, 55]. Bupropion promotes weight loss [56]: in a meta-analysis of five trials of bupropion, the mean difference in weight loss was 2.77 kg (CI, 1.1 to 4.5) between bupropion and placebo groups at 6 months. White and [name] [95] reported preliminary, modest support for weight loss specifically in patients with obesity and BED.

**NB Combination.** The putative mechanisms of action for NB is especially relevant for reducing binge eating and weight per hypothesized effects on brain regions implicated in the regulation of food intake and weight based on research on the mechanisms of action of leptin [94]. The anorectic effects of leptin result from its excitatory effects on pro-opiomelanocortin (POMC) neurons in the hypothalamus melancortin system [96, 97]. Stimulated POMC signaling decreases food intake, increases energy expenditure, but is then inhibited by endogenous feedback [96]. Thus, combining these two drugs will stimulate POMC neurons (bupropion) plus block endogenous feedback that inhibits POMC activity (naltrexone) [47, 94]. This synergistic model received support both in vitro and in vivo studies [47, 98].

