**Obesity Outcomes.** Recently, several large RCTs have reported that the combination of these two medications (Naltrexone/Bupropion) were effective in promoting weight loss in obese patients [47-49, 99]. These RCTs reported significant clinically-meaningful weight losses with sustained-release naltrexone (32 mg/day) plus sustained-release bupropion (360 mg/day) combined in fixed-dose pills. Most recently, Apovian, Aronne [50], in a study of 1496 obese patients reported significantly greater weight losses relative to placebo (-6.5% vs -1.9% at week 28 and -6.4% vs -1.2% at week 56) and significantly greater likelihood of achieving 5% weight loss (56% vs 18% at 28 weeks and 51% vs 17% at 56 weeks). These findings supporting NB medication are quite consistent with earlier (large) RCTs which reported the following percentage of patients achieving at least 5% weight loss: 56% vs. 18% [48]; 52% vs. 15% [100]. Thus, the proposed RCT study will test the effectiveness of Naltrexone/Bupropion relative to placebo for reducing binge-eating and producing weight loss in obese patients with BED.

**Risks.** Several large-scale studies have found that this medication is safe and effective for the treatment of obesity [47-49, 99]. The NB combination approved by the FDA (Contrave) is reported to have the following common adverse reactions: nausea (32.5%), constipation (19.2%), headache (17.6%), vomiting (10.7%), dizziness (9.9%), insomnia (9.2%), dry mouth (8.1%), and diarrhea (7.1%). In addition, Contrave will have the FDA warnings and precautions: Suicidal Behavior and Ideation: Monitor for depression or suicidal thoughts. Discontinue Contrave if symptoms develop. Risk of seizure may be minimized by adhering to the recommended dosing schedule and avoiding co-administration with high-fat meal. Increase in Blood Pressure and Heart Rate: Monitor blood pressure and heart rate in all patients, especially those with cardiac or cerebrovascular disease. Hepatotoxicity: Cases of hepatitis and clinically significant liver dysfunction observed with naltrexone exposure. Angle-closure glaucoma: Angle-closure glaucoma has occurred in patients with untreated anatomically narrow angles treated with antidepressants. Use of Antidiabetic Medications: Weight loss may cause hypoglycemia. Monitor blood glucose.

2. **Source:** Identify the source of the drug or biologic to be used.

Both NB and LDX will be purchased using funds awarded in this grant.

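### Naltrexone/bupropion is given as 50/300 mg generics while its dosing and risk statements lean on a 32/360 mg sustained-release product, and only one liver panel is scheduled during that treatment

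*Combined protocol and SAP*

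**What the plan says.** **Regimen given.** The NB Pharmacotherapy Treatment Protocol (Section I, item 4) says "NB medication will comprise naltrexone (50 mg/day) combined with bupropion (300 mg/day) taken daily". Its day-by-day table names bupropion XL capsules. Section II repeats the dose and adds that the components are generics: "NB medication will combine the generics naltrexone (50 mg/day) combined with bupropion (300 mg/day) taken daily".

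**Regimen cited.** The Background on NB says the supporting trials used "sustained-release naltrexone (32 mg/day) plus sustained-release bupropion (360 mg/day) combined in fixed-dose pills", and that FDA approval followed those trials. Section II describes the cited trials in the same way.

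**Statements that link the two.** The treatment protocol says "NB will be prescribed per FDA-approval for obesity and previous RCTs demonstrating effectiveness for weight loss in obese patients". Minimizing Risks (item 11) says that the NB protocol "follows the evidence-based dosing that has demonstrated safety, tolerability, and efficacy for obesity treated over much longer periods of time". The Data and Safety Monitoring Plan (item 12) argues that the established record of LDX and "Naltrexone/Bupropion (FDA-approval of Contrave for obesity) medications in RCTs suggest that the study procedures and medications are not high risk".

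**Liver monitoring.** The Assessments paragraph of item 11 says the study physician will review a hepatic panel before treatment starts and over its whole course. The same paragraph sets the Stage 2 repeat at the month-1 visit for non-responders. In Figure 2, Liver Function is marked at baseline, month 3 and month 4 (non-responders only), and nowhere later.

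**The concern.** Two separate things look wrong.

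First, an ethics board or safety monitor reading the dosing-basis and risk-level statements would take it that the regimen in the NB arm is the one with the approval and the trial record. By the protocol's own description it differs in daily dose of both components and in formulation. The label adds to the confusion: the Background defines the NB name as the 32/360 mg product, and the treatment protocol then uses it for 50/300 mg. No reason for the change is printed.

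Second, the protocol lists a liver warning for naltrexone, the component dosed above the cited product. If the grid is followed, no liver value is scheduled after the first month on NB, and none at the end. The rule that out-of-range values are flagged at once can act only on a panel that is drawn.

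At stake are the accuracy of the risk description in a study rated greater than minimal risk, and the chance of noticing a late liver-enzyme rise. No effect estimate or test is at stake.

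**Working it through.** There is no power or alpha figure to reproduce. The check is a comparison of sections with simple arithmetic.

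**1. Dose.** Inputs: 50 and 300 mg/day (NB treatment protocol; Section II) against 32 and 360 mg/day (Background; Section II).
- Naltrexone: 50/32 = 1.56, so 56% higher.
- Bupropion: 300/360 = 0.83, so 17% lower.
- Form: separate generic capsules, bupropion as XL, against sustained-release fixed-dose pills.

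These ratios compare milligrams across release forms. They measure a difference in dose, not in exposure or risk.

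**2. Which statements depend on a match.** The three linking statements quoted above use the approval or the trials to support this study's dosing or risk level, so they depend on it. Other NB safety statements do not. In Risks (item 10), "NB has demonstrated safety, tolerability, and efficacy for patients with obesity treated over much longer periods of time" introduces published results. In Section II, "this medication is safe and effective for the treatment of obesity" is given as a finding of earlier large studies, and the adverse-reaction rates that follow are attributed to Contrave. The IND-exemption item on dosage level is a template box that, as printed, asks for no reason. None of these needs correction.

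**3. Liver panels on NB.** NB starts after month 3 and runs for 12 weeks to month 6. Figure 2 marks for Liver Function:
- baseline: before NB
- month 3: before NB
- month 4: on NB
- months 5 and 6, and follow-ups: none

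That makes one panel on NB. The text in item 11 agrees with the grid, so a broken table does not explain the gap.

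**4. Time after the last panel.** The documents do not give the week of the month-1 visit.
- Week 4 (assumed): 12 - 4 = 8 weeks, 8/12 = 67%.
- Week 5: 12 - 5 = 7 weeks, 58%.
- Week 3: 12 - 3 = 9 weeks, 75%.

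**5. How many participants.** The Power Analysis expects 65-70% responders and about 80 people. This is reproduced on the 120 assigned to LDX or CBT+LDX: 120 x 0.65 = 78 and 120 x 0.70 = 84. If everyone else is a non-responder, 120 x 0.30 = 36 to 120 x 0.35 = 42, both arms together. This is an expected number, not a maximum. If the plan's 20% dropout (24 of 120) all falls outside the 78 to 84 responders, 120 - 24 - 84 = 12 to 120 - 24 - 78 = 18 remain. The Stage 2 exclusions for non-responders (history of anorexia or bulimia nervosa, sensitivity to either drug, opioid use) lower the number further.

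**6. Blood at month 6.** Figure 2 already marks lipid profile, HbA1c and glucose at month 6, so a liver panel there needs no extra draw or visit.

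**The case against.** The other side has a good deal that stands.

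- **The dose is not hidden.** It appears twice in text and once in a table, and the 32/360 mg product is also described twice. A careful reader can see both. The fault is loose wording in three places, not concealment.
- **The approved label dose is not printed.** A reader might infer that the trial departs from the approved dose. The documents tie approval to the 32/360 mg trials but do not state the label, so they support only that the regimen differs from the one those trials used.
- **Risk at 50/300 mg is unknown here.** A reader might infer from the 56% figure that liver risk is raised. Nothing in the documents shows that, in either direction, so they give no ground to dispute the IND-exemption box either.
- **The general sentence on hepatic panels can be read across both stages.** Baseline, month 3 and month 4 would then satisfy it. A reader might call the schedule a broken promise, but that reading is not forced. What remains on any reading is one panel on NB and none at its end.
- **Other safeguards exist.** Entry excludes cirrhosis, hepatic failure, and AST above 144 or ALT above 165. A panel at month 3 precedes NB. Out-of-range values go to the study physician, who may stop the drug. The dose can be reduced for intolerable side effects. Clinician visits are monthly, and adverse events are collected at months 4, 5 and 6.
- **No required frequency is set.** The documents fix no interval for liver testing on naltrexone, and a month-6 result comes too late to change dosing. It can detect a rise for follow-up, but it cannot prevent one.

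**Conclusion.** The point holds in a limited form and is minor. The NB arm uses a different dose and release form from the trials cited for it, and three statements carry that evidence over without saying so. One liver panel is scheduled in 12 weeks on NB. About 8 weeks follow it (range 7 to 9, depending on whether the visit falls at week 5, 4 or 3), and there is no end-of-treatment value for a hazard the protocol itself names.

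The documents do not support the stronger conclusions that the regimen is less safe than the cited product, that the dose was concealed, or that liver safety is unmonitored. The NB aim is exploratory, and its randomised comparison with placebo is not affected by either issue.

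**What to change.** 1. In Figure 2, mark Liver Function at month 6 for all Stage 2 non-responders, in both arms so that the blind is kept, on the blood already drawn. In the Assessments paragraph of item 11, replace the general wording with the actual schedule: month 3 before NB or placebo, Stage 2 month 1, and month 6. The cost is one assay per non-responder: roughly 36 to 42 if 30-35% of 120 are non-responders, and fewer after Stage 1 dropout and Stage 2 exclusions. No extra draw or visit is needed.

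2. In the NB treatment protocol, the NB paragraph of item 11 and the Data and Safety Monitoring Plan, say that the cited approval and trial data come from the 32/360 mg sustained-release product and that this study uses 50/300 mg generics. The cost is a few sentences.

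Dosing, randomisation, sample size and analysis stay as they are.
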